9.4.1. Primary Analyses

For the primary efficacy analysis, the difference between the two randomized arms for the proportion of participants with HIV-1 RNA ≥ 50 c/mL at Month 12 (OLI and BIK)/Month 11 (D2I) (according to FDA snapshot algorithm) and its confidence interval will be calculated and be adjusted to the study stratifications using Cochran-Mantel Haenszel (CMH) weights. All CIs will be two-sided. For this analysis, four strata will be formed according to the combinations of levels of the study stratification factors:

- Gender at birth: female
- Gender at birth: male
- BMI: <30 kg/m²
- BMI: ≥ 30 kg/m²

The CMH estimate of the common difference in rates across strata will be calculated as the weighted average of the strata-specific estimates of the difference in response rates between the two arms as follows:

If n_k is the number of CAB LA + RPV LA treated participants, m_k is the number of BIK treated participants, and $N_k = n_k + m_k$ is the total number of participants in the k th stratum, then the CMH estimate is given by

$$\hat{d}_{cmh} = \frac{\sum W_k \hat{d}_k}{\sum W_k}$$

where

$$W_k = \frac{n_k m_k}{N_k}$$

are CMH weights and \hat{d}_k are estimates of the differences in response rates between the two treatment arms, $p_c - p_b$, for the k th stratum. The corresponding two-sided 95% CI will be calculated as:

$$\hat{d}_{cmh} \pm 1.96 \times \sqrt{\hat{\text{var}}(\hat{d}_{cmh})}$$

using the variance estimator $\hat{\text{var}}(\hat{d}_{cmh})$, given by [Sato, 1989], which is consistent in both sparse data and large strata. The full equation for this variance estimate will be provided in the statistical analysis plan.

Female participants randomized to CAB + RPV LA who become pregnant while in the study are allowed to continue. Female participants randomized to BIK will not be allowed to continue. For the FDA snapshot algorithm-related efficacy analysis at key time points (Month 5/6 and Month 11/12), viral load data after confirmed pregnancy may be “censored”, to minimize bias between the treatment and the comparator arm. Further sensitivity analysis may be performed as necessary. Data handling details will be provided in the Reporting Analysis Plan.

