9.2. Sample Size Considerations

9.2.1. Sample Size Determination

Sample size was determined based on desired study power. A total of 654 enrolled participants will be randomized in a 2:1 ratio to receive either CAB LA + RPV LA or BIK treatment. Assuming the true proportion of participants with HIV-RNA ≥ 50 c/mL is 2% for CAB LA+RPV LA injectable regimen and 1% for the BIK arm, a non-inferiority margin of 4% and a 2.5% one-sided significance level, the study will provide approximately 85% power to demonstrate non-inferiority of CAB LA+RPV LA to BIK in term of proportions participants with HIV-1 RNA ≥ 50 c/mL at Month 12 (per FDA's snapshot algorithm for assessing HIV-1 RNA ≥ 50 c/mL). Details of this calculation along with a couple of another sample size scenarios were provided in [Table 7](#).

Note: "Enrolled" means a participant's, or their legally acceptable representative's, agreement to participate in a clinical study following completion of the informed consent process. Potential participants who are screened for the purpose of determining eligibility for the study, but do not participate in the study, are not considered enrolled, unless otherwise specified by the protocol.

Assuming a possible 15% of screen failure, a total of ~770 would need to be recruited to achieve ~654 participants to be enrolled and randomized.

Table 7 Sample Size and Power Scenarios

Assumptions			Sample Size		Power* to reject H_0 at $\alpha=2.5\%$
p_c	p_b	NI Margin	CAB LA+RPV LA	BIK	
2%	1%	4%	390	195	80%
2%	1%	4%	436	218	85%
2%	1%	4%	509	255	90%

* Power was calculated using PASS 2019 Non-inferiority Tests for the Difference Between Two Proportions with Miettinen & Nurminen Likelihood Score Test Statistics.

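### The stated 85% power belongs to a score test; the planned ±1.96 × SE interval has about 89–90% power, and its one-sided error exceeds 2.5% only if BIK failures are rarer than about 1%

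*Protocol*

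**What the plan says.** Section 9.2.1 of the protocol sets the size: "A total of 654 enrolled participants will be randomized in a 2:1 ratio", which Table 7 splits as 436 and 218. The assumed failure rates are "2% for CAB LA+RPV LA injectable regimen and 1% for the BIK arm", with "a non-inferiority margin of 4% and a 2.5% one-sided significance level". On these inputs "the study will provide approximately 85% power to demonstrate non-inferiority of CAB LA+RPV LA to BIK". The footnote to Table 7 names the method: "Power was calculated using PASS 2019 Non-inferiority Tests for the Difference Between Two Proportions with Miettinen & Nurminen Likelihood Score Test Statistics".

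Section 9.1 concludes non-inferiority when the upper 95% limit for CAB LA + RPV LA minus BIK lies below 4%. Section 9.4.1 then fixes that limit. Four strata (sex at birth by BMI below or at least 30) are combined with CMH weights, and the interval follows: "The corresponding two-sided 95% CI will be calculated as" the weighted difference ± 1.96 × √variance. The variance is the Sato estimator, described as one "which is consistent in both sparse data and large strata". Only its full equation is left to the statistical analysis plan; the shape of the interval and the choice of variance are already fixed.

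**The concern.** Two different procedures stand in one protocol: a score test for sizing and a symmetric normal interval for the decision. Nothing reconciles them.

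The difference matters because events are rare. At a 1% rate, 218 BIK participants yield about 2 expected failures. The score method takes its standard error under the null difference of 4%. The Sato interval takes it from the observed rates, so when the BIK arm shows no failures that arm adds nothing to the standard error. The upper limit can then be too low, in the direction of a false non-inferiority claim, and it happens when the comparator has done best. Consistency of the variance is a large-sample property and does not make the interval accurate with two expected events.

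At stake are whether the power statement describes the planned analysis, and whether the 2.5% one-sided level is held if BIK performs better than assumed.

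**Working it through.** **Inputs.** From 9.2.1: n = 436, m = 218, rates 2% and 1%, margin 4%, one-sided 2.5%. From 9.1 and 9.4.1: the decision rule, interval and four strata. From 4.2: about 20% women. The share with BMI ≥ 30 is not given; 20–30% is assumed.

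**Rules compared.** Let x and y be the failures on CAB LA + RPV LA and BIK.
- Planned: d + 1.96 × √var < 4%. The Sato variance is (d·ΣPₖ + ΣQₖ)/(ΣWₖ)², with Pₖ = [nₖ²yₖ − mₖ²xₖ + nₖmₖ(mₖ − nₖ)/2]/Nₖ² and Qₖ = [xₖ(mₖ − yₖ) + yₖ(nₖ − xₖ)]/(2Nₖ). With one stratum it equals the unpooled Wald variance to numerical precision.
- Score: (d − 4%)/SE₀ < −1.96, where SE₀ uses rates estimated under a difference of 4% and the factor N/(N − 1).

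**Step 1: the plan's own figure.** Exact binomial enumeration at 2% vs 1%, one stratum:

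| n / m | Stated | Score test | Planned interval |
|---|---|---|---|
| 390 / 195 | 80% | 81.1% | 88.0% |
| 436 / 218 | 85% | 85.1% | 89.6% |
| 509 / 255 | 90% | 90.8% | 94.8% |

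Table 7 reproduces for the score test and not for the planned interval. A four-stratum simulation of the planned interval gives 89.4%; a stratified score interval gives 84.0%.

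**Step 2: one-sided error at 436/218 with p_c = p_b + 4%.** The four-stratum column comes from 1,000,000 simulated trials per setting, with BMI ≥ 30 at 20% and at 30%.

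| BIK rate | Planned, one stratum (exact) | Planned, four strata | Score, unstratified (exact) |
|---|---|---|---|
| near 0 (limit) | 6.5% | 5.6–6.2% | 1.9% |
| 0.25% | 4.4% | 4.0–4.3% | 2.1% |
| 0.5% | 3.35% | 3.2–3.3% | 2.3% |
| 0.75% | 2.8% | 2.8% | 2.4% |
| 1.0% | 2.53% | 2.50–2.53% | 2.4% |
| 1.1% | 2.46% | – | 2.4% |
| 1.7% | 2.25% | – | 2.4% |
| 2.0% | 2.2% | 2.2% | 2.5% |
| 3.0% | 2.04% | 2.1% | 2.65% |

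In the one-stratum calculation the planned interval crosses 2.5% at a BIK rate of 1.04%.

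**Step 3: where the decision changes (one stratum).** Take 0 BIK failures and 11 on CAB LA + RPV LA.
- Planned: 11/436 = 2.523%; SE = √(0.02523 × 0.97477/436) = 0.751%; upper limit = 2.523% + 1.96 × 0.751% = 3.995%. Passes.
- Score: the restricted rates are 4% and 0%, so SE₀ = √(0.04 × 0.96/436 × 654/653) = 0.939%; z = (2.523 − 4)/0.939 = −1.57. Fails. With 9 failures z = (2.064 − 4)/0.939 = −2.06, which passes; with 10, z = −1.82, which fails.

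So with 0 BIK failures the planned rule accepts up to 11 and the score test up to 9. With 1 BIK failure it is 11 against 10. From 2 to 6 they agree. At some higher counts the score test is the more lenient by one failure, which is why the error columns swap order at higher rates.

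**Step 4: how often BIK shows no failures.** 0.99²¹⁸ = 11%; 0.995²¹⁸ = 34%.

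**The case against.** The planned interval is sound wherever the protocol supplies a figure. Table 8 gives BIK rates of 1.1% and 1.7%, pooled 8/572 = 1.4%, and 9.2.2.1 cites 1–3% as typical for switch studies. From 1.1% to 3% the exact error lies between 2.46% and 2.04%, and at the planning value of 1% it is 2.53%. No document figure supports 0.5% or 0.25%. The excess error also needs a true CAB LA + RPV LA rate above 4%, against 1.7% (9/522) in the cited long-acting trial. The score test itself reaches 2.65% at a BIK rate of 3%, so the choice is between two accepted methods with different weak spots. Sizing with the stricter method harms no one, since it understates power.

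All of that stands, and it limits the point. It does not remove it. The planning rate sits almost on the crossing point, so there is no margin on the low side. A lower BIK rate is plausible: inclusion criterion 5 requires at least 6 months of uninterrupted BIK with suppression, and section 5.2 excludes prior treatment failure, whereas the BIK rates in Table 8 come from studies of people switching to BIK. Section 9.2.3 itself treats the BIK rate as uncertain.

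A reader might infer that the trial is underpowered, or that the 2.5% level already fails under the design assumptions. The documents support neither: power under the planned rule is above the stated figure, and the error at 1% is nominal.

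**Conclusion.** The point holds in a limited form and is worth correcting. First, the 85% describes an unstratified score test, not the stratified Sato interval that decides the trial, whose power at 2% vs 1% is about 89–90%. This is a misstatement of power, not a shortfall. Second, the planned interval's one-sided error is nominal at the planning rate and conservative at the cited historical rates, but exceeds 2.5% below a BIK rate of about 1%, reaching about 3.3% at 0.5%. The value of about 6% at a rate of zero is a limit, not a planning scenario.

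The planned rule is the more lenient one only when BIK has 0 or 1 failures, by two and one long-acting failures respectively. The power result rests on the protocol's inputs; the error excess rests on the assumption that BIK does better than planned. The assumed BMI split moves the results little.

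**What to change.** Keep the CMH-weighted point estimate. What follows depends on whether data grouped by arm have been reviewed; sections 6.3.2 and 9.4 place this at the Month 6 interim.

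- **Not yet reviewed:** in 9.4.1, make the stratified Miettinen-Nurminen interval with the same CMH weights the one judged against 4%. Keep the Sato interval as a sensitivity analysis. State power in 9.2.1 as about 84% for the stratified score analysis.
- **Already reviewed:** changing the primary rule would raise a credibility problem of its own. Keep the Sato interval as primary, restate its power as about 89%, and add the stratified score interval as a prespecified sensitivity analysis.

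The change needs protocol and analysis-plan wording and standard software, and no more participants. Its price is about 5 points of power against what the Sato rule has (89.4% to 84.0%). The loss is larger if BIK does better: at 2% vs 0.5%, one stratum, 85.6% falls to 75.3%. The score test also runs slightly above 2.5%, up to about 2.65%, at BIK rates of 2–3%.

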9.4.2. Safety and Secondary Analyses

The proportion of participants with plasma HIV-1 RNA <50 c/mL using the Snapshot algorithm is a key outcome at Months 6 and 12 (OLI and BIK)/Months 5 and 11 (D2I) and will be judged against a pre-specified non-inferiority margin of -12%.

Changes from baseline in CD4+ lymphocyte count and in CD4+/CD8+ lymphocyte counts ratio and resistance data will be summarized. The incidence of HIV-1 disease progression (AIDS and death) will be presented.

The proportion of participants with plasma HIV-1 RNA <50 c/mL using the Snapshot algorithm and changes from baseline in CD4+ lymphocyte count will be summarized by subgroups (e.g., age, gender and race)

The observed case dataset will be the primary dataset used for analysis of safety endpoints.

Exposure to study medication, measured by the number of weeks on study drug, will be summarized by treatment group. The proportion of participants reporting AEs will be tabulated for each treatment group. The following summaries of AEs will be provided:

- Incidence and severity of all AEs
- Incidence and severity of treatment related AEs
- Incidence and severity of AEs leading to withdrawal
- Incidence of SAEs

CCI

Laboratory and vital signs data will be summarized by visit and treatment group. In addition, the number and percentage of participants with graded laboratory toxicities (based on DAIDS categories) will be summarized by treatment group. The proportion of participants experiencing changes from Baseline in their National Cholesterol Education Program (NCEP) lipid categories will be summarized by treatment arm. Further details of safety analyses will be included in the RAP.

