1.2. Schema

1.3. Schedule of Activities (SoA)

Time and Events Table for CAB LA + RPV LA Oral Lead In (OLI) Participants:

Procedure	Screening Visit ^a	Maintenance Phase								Extension Phase	Withdrawal Assessments ^y	Long-Term Follow-up ^z	
		Day 1 ^b	Month										
			1 ^c	2	4	6	8	10	12				Q2M after Month 12
Written Informed Consent	X												
Eligibility Verification (Inclusion/ Exclusion Criteria)	X	X ^d											
Randomization		X											
Demography	X												
Medical History ^e	X												
Cardiovascular risk assessment ^e	X	X							X		X		
Medication History/ Prior ART history	X												
Syphilis serology + reflex Rapid Plasma Reagin (RPR)	X	X											
Symptom Directed Physical Exam and Medical Assessment ^f	X	X	X	X	X	X	X	X	X	X	X	X	
Weight, Height and BMI ^g		X		X	X	X			X		X		
Waist Circumference		X		X	X	X			X		X		
Hip Circumference		X		X	X	X			X		X		
Vital Signs (BP, HR, Temperature) ^h	X	X		X	X	X			X		X		
CCI													
12-lead ECG ⁱ (triplicate at Day 1 pre-dose)	X	X	X						X		X		
CDC HIV-1 stage ^h	X	X											
HIV Associated Conditions		X	X	X	X	X	X	X	X	X	X	X	
AEs, SAEs, Concomitant Medications	X	X	X	X	X	X	X	X	X	X	X	X	
ISR Assessment for IM injection			X	X	X	X	X	X	X	X	X	X	

Procedure	Screening Visit ^a	Maintenance Phase								Extension Phase	Withdrawal Assessments ^y	Long-Term Follow-up ^z	
		Day 1 ^b	Month										Q2M after Month 12
			1 ^c	2	4	6	8	10	12				
Columbia Suicide Severity Rating Scale (eC-SSRS) ^k	X	X		X		X			X		X		
Clinical chemistry and Hematology	X	X	X	X	X	X	X	X	X	X	X	X	
Pregnancy Testing ^l	S	U	U	U	U	U	U	U	U	U	S	U	
HIV-1 RNA and sample for storage (S) ^m	X	X	X	X	X	X	X	X	X	X	X	X	
HIV-1 RNA low copy sample		X							X				
CD4+ cell count	X	X	X	X	X	X	X	X	X	X	X	X	
CD8+ cell count		X				X			X		X		
Urinalysis ⁿ		X	X			X			X		X		
Fasting Labs Glucose, Cholesterol (Total, HDL and LDL) and Triglycerides ^o		X				X			X		X ^p		
Hepatitis B (HBsAg), Anti-HBc, and Anti-HBsAG, Hepatitis C (anti-HCV Ab)	X												
PT/PTT/INR	X	X											
Whole Blood (Virology)		X				X			X		X		
CCI													
PBMCs ^q		X				X			X		X		
Insulin, HbA1c and renal, and bone biomarker analytes (blood urine) ^r		X				X			X		X ^s		
CCI													
Genetics sample ^t		X											
PK sampling ^u (S)=Storage only			S	S	S	S	S	S	S		X	S	
Oral CAB and Oral RPV Dispensation ^v		X											

Procedure	Screening Visit ^a	Maintenance Phase								Extension Phase	Withdrawal Assessments ^y	Long-Term Follow-up ^z	

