PT/PTT/INR	X	X										
Whole Blood (Virology)		X			X			X		X		
CCI												
PBMCs ^q		X			X			X		X		
Insulin, HbA1c and renal, and bone biomarker analytes (blood urine) ^r		X			X			X		X ^t		
CCI												
Genetics sample ^t		X										
PK sampling ^u (S)=Storage only			S	S	S	S	S	S		X	S	
IM treatment administration		X	X	X	X	X	X	X	X			
HIV TSQs ^{cc}		X			X			X		X ^{dd}		
HIV TSQ ^{cc}								X		X ^{dd}		
CCI												
Preference ^{cc}								X		X ^{dd}		
PIN ^{cc}			X		X			X		X ^{dd}		
CCI												
History of Cosmetic procedures ^{gg}								X		X		

Time and Events Table for BIK Participants:

Procedure	Screening Visit ^a	Maintenance Phase							Withdrawal Assessments ^y
		Day 1 ^b	Month						
			2	4	6	8	10	12 ^{bb}	
Written Informed Consent	X								
Eligibility Verification (Inclusion/ Exclusion Criteria)	X	X ^d							
Randomization		X							
Demography	X								
Medical History ^e	X								
Cardiovascular risk assessment ^e	X	X						X	
Medication History/ Prior ART history	X								
Syphilis serology + reflex Rapid Plasma Reagin (RPR)	X	X							
Symptom Directed Physical Exam and Medical Assessment ^f	X	X	X	X	X	X	X	X	X
Weight, Height and BMI ^g		X	X	X	X			X	X
Waist Circumference		X	X	X	X			X	X
Hip Circumference		X	X	X	X			X	X
Vital Signs (BP, HR, Temperature) ^h	X	X	X	X	X			X	X
CCI									
12-lead ECG ^j (triplicate at Day 1 pre-dose)	X	X						X	X
CDC HIV-1 stage ^{ff}	X	X							
HIV Associated Conditions		X	X	X	X	X	X	X	X
AEs, SAEs, Concomitant Medications	X ⁱ	X	X	X	X	X	X	X	X
Columbia Suicide Severity Rating Scale (eC-SSRS) ^k	X	X	X		X			X	X
Clinical chemistry and Hematology	X	X	X	X	X	X	X	X	X
Pregnancy Testing ^l	S	U	U	U	U	U	U	U	S
HIV-1 RNA and sample for storage (S) ^m	X	X	X	X	X	X	X	X	X

Procedure	Screening Visit ^a	Maintenance Phase						Withdrawal Assessments ^y	
		Day 1 ^b	Month						
			2	4	6	8	10		12 ^{bb}
HIV-1 RNA low copy sample		X					X		
CD4+ cell count	X	X	X	X	X	X	X	X	
CD8+ cell count		X			X		X	X	
Urinalysis ⁿ		X			X		X	X	
Fasting Labs Glucose, Cholesterol (Total, HDL and LDL) and Triglycerides ^o		X			X		X	X ^p	
Hepatitis B (HBsAg), Anti-HBc, and Anti-HBsAG, Hepatitis C (anti-HCV Ab)	X								
PT/PTT/INR	X	X							
Whole Blood (Virology)		X			X		X	X	
CCI									
PBMCs ^q		X			X		X	X	
Insulin, HbA1c and renal, and bone biomarker analytes (blood urine) ^r		X			X		X	X ^x	
CCI									
Genetics sample ^t		X							
BIK Dispensation		X	X	X	X	X	X	X ^{aa}	
IP accountability (Pill Counts)			X	X	X	X	X		
HIV TSQ ^{scc}		X			X		X	X ^{dd}	

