- f. Physical exams should be conducted as part of normal routine clinical care. Medical assessments include any decisions the study staff must make for participants management and/or care of participant.
- g. Height collected at Baseline Day 1 only. Recommended procedures to measure weight, waist and hip circumference can be found in Section 10.10. Weight related measurements to be collected are weight, body fat %, total body water %, muscle mass, and bone mineral mass.
- h. Measure vital signs after about 5 minutes of rest in a semi-supine position.
- i. A 12-lead ECG will be performed after resting in a semi-supine position for at least 5 minutes. ECGs will be performed pre-dose. ECG pre-dose will be performed in triplicate at Day 1. A 2-hour post-dose ECG will also be performed at Day 1 (D2I), Month 1 (OLI) and Month 12 (OLI)/Month 11 (D2I) for participants receiving CAB LA + RPV LA with an allowable window of ± 30 minutes.
- j. Only SAEs related to study participation or to a concomitantly administered ViiV/GSK product will be collected between obtaining informed consent and administration of study drug at Day 1.
- k. On Day 1, the eC-SSRS is to be administered prior to randomization. The eC-SSRS will be completed at the beginning of the visit following administration of other PROs required prior to injections. The eC-SSRS is not required during the Withdrawal visit if withdrawal occurs during the Extension Phase.
- l. Women of childbearing potential only. S=serum, U=urine. Pregnancy events will be captured starting at Day 1 following initial exposure to study drug. Serum pregnancy test can substitute for urine pregnancy test if locally required but must be appropriately timed to confirm pregnancy status prior to randomization and first IM administration. If the urine test is positive, perform a serum test and do not administer injection. The frequency of pregnancy tests should be performed according to local legal requirements.
- m. Month 12 (OLI and BIK) and Month 11 (D2I) HIV-1 RNA retest (within 4 weeks) for results > 50 c/mL will be captured as unscheduled visit. Plasma for storage samples will be used for possible future analyses.
- n. A morning specimen is preferred. To assess biomarkers: urine albumin/creatinine ratio; urine protein/creatinine ratio; urine phosphate; beta-2-microglobulin; and retinol binding protein.
- o. An overnight fast is preferred; however, a minimum of a 6-hour fast is acceptable.

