To assess preference for CAB LA + RPV LA administered every 2 months compared to a BIK single tablet regimen administered once daily	Preference for CAB LA + RPV LA every 2 months compared to a BIK single tablet regimen will be assessed using a preference questionnaire at Month 12 (OLI)/Month 11 (D2I) (or Withdrawal).

Objectives	Endpoints

To assess patient reported treatment satisfaction, and injection tolerability.
	
Change from baseline (Day 1) in total “treatment satisfaction” score, and individual item scores of the HIV Treatment Satisfaction Status Questionnaire (HIVTSQs) at Month 6 and Month 12 (OLI and BIK)/Month 5 and Month 11 (D2I), (or Withdrawal)
 
Change in treatment satisfaction over time using the HIV Treatment Satisfaction Change Questionnaire HIVTSQc total score and individual item scores at Month 12 (OLI and BIK)/Month 11 (D2I) (or Withdrawal).
 
Change from Month 2 in Dimension scores (“Acceptance of ISRs”, “Bother of ISRs”, “Leg movement”, “Sleep”) and individual item scores (assessing pain during injection, anxiety before and after injection, willingness to be injected in the future and overall satisfaction with mode of administration over time) will be assessed using the Perception of injection questionnaire (PIN) at Months 2, 6, and 12 (OLI)/Months 1, 5, 11 (D2I) (or Withdrawal)

Safety
	

To evaluate the safety and tolerability of CAB LA + RPV LA every 2 months compared to a BIK single tablet regimen administered once daily
	
Incidence and severity of AEs and laboratory abnormalities over time including Month 6 and Month 12 (OLI and BIK)/Month 5 and Month 11 (D2I).
 
Proportion of participants who discontinue treatment due to AEs over time including Month 6 and Month 12 (OLI and BIK)/Month 5 and Month 11 (D2I).
 
Change from Baseline in laboratory parameters over time including Month 6 and Month 12 (OLI and BIK)/Month 5 and Month 11 (D2I).

CCI

CCI

CCI

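### Minor, urinalysis only: Section 9.4.2 counts participants with graded laboratory toxicities by arm, but three urinalyses are scheduled after Day 1 on CAB LA + RPV LA and two on BIK

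*Protocol*

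**What the plan says.** Among the safety endpoints, Protocol Section 3 lists "Incidence and severity of AEs and laboratory abnormalities over time", under an objective that compares the injectable regimen with BIK. Section 9.4.2 plans two laboratory displays. The first is by visit: "Laboratory and vital signs data will be summarized by visit and treatment group". The second is introduced as an addition to the first and is at participant level: "the number and percentage of participants with graded laboratory toxicities (based on DAIDS categories) will be summarized by treatment group". No visit restriction is attached to it. The paragraph closes with "Further details of safety analyses will be included in the RAP".

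Section 8.2.2 has the central laboratory grade results automatically on the DAIDS scales. The DAIDS table in Section 10.4 includes a urinalysis block with grades for glycosuria, haematuria and proteinuria, so urine results can enter the graded summary.

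The urinalysis rows in the Section 1.3 tables differ between arms. Each injectable table reads "Urinalysis ⁿ X X X X X" (Day 1, Month 1, two later visits, Withdrawal). The BIK table reads "Urinalysis ⁿ X X X X" (Day 1, Month 6, Month 12, Withdrawal). BIK has no Month 1 visit.

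**The concern.** The percentage of participants with at least one graded result rises with the number of samples taken. For urinalysis, the extra Month 1 sample exists only in the injectable arm. A participant-level count over all post-baseline visits would therefore tend to show more graded urine abnormalities on CAB LA + RPV LA even if the true rates were equal. The distortion runs one way: under equal rates it can vanish but cannot favour the injectable arm. At stake is how one block of a descriptive safety table is read. A reader could take a modest excess of proteinuria, glycosuria or haematuria as a drug effect, or fail to see a difference in the other direction.

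**Working it through.** The protocol states no figure for this quantity, so there is nothing of its own to reproduce.

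**Step 1. Scheduled tests after Day 1, Maintenance Phase (Section 1.3 tables)**

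| Assessment | Oral lead-in | Direct to injection | BIK |
|---|---|---|---|
| Urinalysis | 3 (Months 1, 6, 12) | 3 (Months 1, 5, 11) | 2 (Months 6, 12) |
| Chemistry/haematology | 7 | 6 | 6 |
| Fasting lipids/glucose | 2 | 2 | 2 |

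The material imbalance in laboratory sampling is in urinalysis. For chemistry/haematology the highest possible ratio is 7/6, about 1.17, for oral lead-in against BIK, and 6/6 = 1.00 for direct to injection.

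**Step 2. Equal rates, independent results**

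Let p be the per-test probability of a graded urine abnormality, the same in both arms. The documents do not give it; I assume 1% to 30%. Then P(at least one in k tests) = 1 − (1 − p)^k, with k = 3 for the injectable arm and k = 2 for BIK. The ratio simplifies to (3 − 3p + p²)/(2 − p), which tends to 1.5 as p tends to 0.

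| p | Injectable (k = 3) | BIK (k = 2) | Ratio |
|---|---|---|---|
| 1% | 2.97% | 1.99% | 1.49 |
| 2% | 5.88% | 3.96% | 1.49 |
| 5% | 14.26% | 9.75% | 1.46 |
| 10% | 27.1% | 19.0% | 1.43 |
| 20% | 48.8% | 36.0% | 1.36 |
| 30% | 65.7% | 51.0% | 1.29 |

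**Step 3. Equal rates, correlated results within a participant**

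Use a beta-binomial model with correlation ρ, also not given in the documents and assumed from 0 to 1. With a = p(1 − ρ)/ρ and b = (1 − p)(1 − ρ)/ρ, P(at least one in k) = 1 − Π (b + i)/(a + b + i), for i = 0 to k − 1.

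Example at p = 5%, ρ = 0.3: a = 0.1167, b = 2.2167, a + b = 2.3333. For k = 2 the product is 0.950 × 0.965 = 0.9167, giving 8.33%. For k = 3, multiply by 4.2167/4.3333 = 0.9731 to get 0.8921, giving 10.79%. The ratio is 10.79/8.33 = 1.30.

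| ρ (p = 5%) | Injectable | BIK | Ratio |
|---|---|---|---|
| 0 | 14.26% | 9.75% | 1.46 |
| 0.1 | 12.99% | 9.27% | 1.40 |
| 0.3 | 10.79% | 8.33% | 1.30 |
| 0.5 | 8.92% | 7.38% | 1.21 |
| 0.7 | 7.25% | 6.42% | 1.13 |
| 1 | 5.00% | 5.00% | 1.00 |

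**Step 4. Restrict to common visits**

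With Months 6 and 12 (oral lead-in and BIK) or Months 5 and 11 (direct to injection), k = 2 in both arms. On scheduled samples the ratio under equal rates is 1.00 for any p or ρ.

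**The case against.** The strongest reply is that the choice of visits feeding a toxicity table belongs in the analysis plan. Section 9.4 calls itself a summary, the paragraph defers safety detail to the RAP, and the RAP was not available. The sentence also does not say that the count is cumulative over all visits. By-visit summaries are planned, and the Section 3 endpoint names Months 6 and 12 (5 and 11 for direct to injection), so a matched reading will be possible. The table carries no test or margin, and any excess would count against the investigational regimen.

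Much of this stands and makes the point minor. It does not remove it. The participant-level count is planned on top of the by-visit display, its natural reading is over all post-baseline results, and the by-visit tables do not correct it.

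A reader might infer more than the documents support:

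- *An excess of 1.5 times is to be expected.* That is the ceiling, reached only for rare and independent results; persistence lowers it to 1.0.
- *Graded laboratory toxicities in general are distorted.* Chemistry/haematology counts are 7, 6 and 6, and fasting tests 2, 2 and 2.
- *The ECG schedule adds to the problem.* The injectable arm does have more tracings ("A 2-hour post-dose ECG will also be performed at Day 1 (D2I), Month 1 (OLI) and Month 12 (OLI)/Month 11 (D2I) for participants" receiving the injections), but DAIDS grades QTc prolongation under cardiovascular conditions, not laboratory values, and Section 9.4.2 specifies no ECG incidence table.
- *The renal biomarker endpoint is biased.* Section 3 sets that endpoint at Months 6 and 12 (5 and 11 for direct to injection), so the timepoints are already matched and the Month 1 sample does not enter.

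**Conclusion.** The point holds as a minor one, for urinalysis only. Applied over all post-baseline visits, the planned count of participants with graded toxicities gives the injectable arm three scheduled urine tests against two on BIK. Under equal true rates the ratio lies between 1.0 and about 1.5; at an assumed 5% per-test rate it is 1.30 at a correlation of 0.3 and 1.21 at 0.5. These figures assume a common per-test rate across visits and arms, full attendance, and no unscheduled samples. The protocol supplies neither the rate nor the correlation, so the range is the result. Nothing here touches the primary analysis, the renal biomarker endpoint, the ECG data or the other graded laboratory tests.

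**What to change.** Add a sentence to Section 9.4.2: the between-arm incidence of graded urinalysis toxicities uses the assessments scheduled in both arms (Months 6 and 12 for oral lead-in and BIK, Months 5 and 11 for direct to injection) plus withdrawal samples, and excludes unscheduled repeats triggered by a Month 1 result. Report the Month 1 urinalysis findings and their repeats alongside, for the CAB LA + RPV LA arm only.

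The exclusion is needed because Section 8.3.11.4 calls for a repeat 2 to 4 weeks after an abnormal urine albumin/creatinine ratio, and Section 8.3.11.3 adds a urinalysis at the confirmatory visit after a creatinine rise. Repeats that follow a Month 1 result can arise only in the injectable arm and would bring the imbalance back.

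The cost is one extra table split, with Month 1-only findings shown outside the comparative column. No assessment is added or dropped and no data are lost.
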